6.1.2 Baseline Definition

For subject who received any dose of study drug, baseline is the last non-missing result prior to first dose including the data collected during the parent study for SES-CD, CDEIS, Calprotectin, CRP and all lab assessment. For subjects who are enrolled into this open-label study but never received any study drug, baseline is either assessment collected at baseline visit if available or screening visit or as specified otherwise.

For fecal calprotectin, the baseline is the last available assessment up to day 3.

6.1.3 Missing Data and Handling of Dropouts

All available outcome and safety data will be included in data listings and tabulations.

CDAI Missing Data:

The computation of CDAI requires 7 days of consecutive diary daily data. For subjects with CDAI diary data reported that is less than 7 days of data, the reported data will be standardized to 7 days by dividing the sum of CDAI score over the number of days of data by total number of days of reported data multiplied by 7. If less than 4 days of diary data is available, the subject will be categorized as a non-responder and the CDAI score will be considered missing. As specified in section 2.2, subjects with missing assessment will be assumed to not be in a state of remission/success for each scheduled visit (week 16, 26, or 52).

Handling of missing date information for AEs:

The term *missing date* refers to a completely missing date or to partial date where month or/and day or/and year is/are missing, e.g. missing month/day/year. Missing start and end dates will be imputed conservatively, i.e. missing values will be imputed in such a way that the duration of the AE is considered with the longest possible duration. The missing start date and end date of AE will be imputed for the purpose of defining treatment emergent adverse events (TEAE) and for assigning events to treatment periods using the following definitions:

(i) Adverse Event Start Date:

Event Missing Day: If Adverse event day is missing but month and year present, then impute the 1st of the month unless month and year are the same as first dose of study drug then impute day first day of dose.

Event Missing day and month – If adverse event day and month both are missing but year is present then impute 1st January unless year is the same as first dose date then impute day and month first dose day and month.

Completely missing – impute first dose date unless the end date suggests it could have started prior to this in which case impute the 1st January of the same year as the end date.

(ii) Adverse Event End Date:

Missing day – If AE day is missing but month and year is present then impute the last day of the month.

Missing day and month – If AE has missing day and month but year is present then impute 31st December.

Completely Missing – Required to look at whether the AE is still ongoing before imputing a date and also when it started in relation to study drug. If the ongoing flag is missing then assume that AE is still present (i.e. do not impute a date). If the AE has stopped and start date is prior to first dose date then impute the 1st dose date, if it started on or after first dose date then impute a date that is after the last dose date.

(iii) TEAE definition with missing start and stop dates: If the start date of an adverse event is incomplete or missing, the event will be assumed to be a treatment-emergent adverse event (TEAE), unless the incomplete start date (month and/or year) or the stop date (complete or incomplete) clearly indicates that the event started prior to dosing. Missing/incomplete information will be reported as missing/incomplete in the subject listings.

(iv) Adverse event relationship: If the relationship for an adverse event is not recorded, it will be assumed to be treatment related in the presentation of the statistical summary of incidence results. Missing information will be reported as missing in the subject listings.

(v) Adverse event severity: If the severity of an adverse event is missing, the severity will be assumed to be severe when summarizing data. Missing information will be reported as missing in the subject listings.

(vi) Non-study medication (concomitant medications, steroids) start and stop dates: If the start and/or stop dates of non-study medication use are incomplete or missing, the use will be assumed to be concomitant, unless the incomplete date information clearly indicates that the use stopped prior to study medication dosing. Missing/incomplete information will be reported as missing/incomplete in the subject listings.

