Study Design:	
This is an open label, multicenter, Phase III, study designed to evaluate the efficacy and safety of RHB-104 to treat subjects with active CD as defined by CDAI \geq 150 despite 26 weeks of treatment with study drug in RedHill Biopharma Study RHB-104-01. RHB-104 consists of 3 antibiotics with activity against Mycobacterium avium subsp. paratuberculosis (MAP), a potential cause of CD. Eligible subjects with active CD who have completed 26 weeks of study drug as part of the RHB-104-01 study will receive up to 52 weeks of open label RHB-104. Subjects enrolled in the open label study may have current CD therapies adjusted or withdrawn as clinically indicated by their local investigator after 8 weeks of open label RHB-104 treatment. Sites should begin tapering steroids upon completion of 4 weeks of RHB-104 treatment with the goal of being steroid free by week 14 – Refer to Appendix 13.
 
MAP are slow growing mycobacteria without a proven antibiotic treatment, and the duration of antibiotic treatment required to achieve remission in subjects with CD caused by MAP is believed to be approximately 16-26 weeks. Subjects with response at week 26 may ultimately achieve remission at a later time point with continued treatment for MAP. Similarly, some subjects may achieve response or achieve remission prior to week 26. This study is designed to assess response, remission, and maintenance of remission in subjects on open label RHB-104 through week 52, as well as corticosteroid free remission at week 16.
 
Blood samples will be collected at Screening and at every visit after the initial 8 weeks of treatment to test for MAP in the serum using a polymerase chain reaction (PCR) assay. Similarly, MAP cultures will be prepared from whole blood collected at Screening and at weeks 16, 26 and 52.
 
Safety of the fixed-dose combination product, RHB-104, will also be assessed.
 
Colonoscopy will be done in consenting subjects at baseline (prior to initiation of open label RHB-104) and after 16 and 52 weeks of open label RHB-104 to assess for mucosal healing as well as MAP status via PCR and culture.
 
Study Visit Schedule:
 
Screening, Baseline, and follow-up visits at weeks 2, 4, 8, 16, 26, 39, 52, and 56. Subjects undergoing colonoscopy will have a procedural visit after week 16 and 52 assessment so as to not interfere with data collection.

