2.2.1 Primary Endpoint/Variable: Remission

In general use of rescue medication is considered as treatment failure (not achieving remission or response) if there are any new use of rescue medication to treat CD or increased rescue medication dose from baseline prior to any remission or response assessment. Please refer to section 6.1.6 for more details.

The primary variable is the proportion of subjects who experienced remission at Week 16 after the initiation of open-label phase, where remission is defined as a subject having a Crohn's Disease Activity Index (CDAI) score of <150 . Subjects who have a Week 16 CDAI measurement ≥ 150 or who do not have a CDAI measurement at Week 16 will be classified as not having achieved remission at that time point. Initiation of open-label phase is the first dosing time of open-label phase and from here and after it would be reference as initiation.

The CDAI is used to assess the activity of CD; higher scores indicate more active disease.

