4.1.1 Study Visit Schedule

	Screening / Opt Screening / Visit Week 26 of RHB-104-01	Baseline Day 1 / Week 0 ²	Week 2	Week 4	Week 8	Week 16	Week 26	Week 39	Week 52	Week 56
Study Visit Window	(up to 21 days before BL if initial colonoscopy is performed)	Up to 21 days post SCR	± 3 days	± 3 days	± 7 days	± 7 days	± 7 days	± 7 days	± 7 days	± 7 days
Informed Consent	X									
Inclusion/ Exclusion Criteria Demography, Medical History	X	X								
Concomitant Medications Assessment		X ³	X	X	X	X	X	X	X	X
Vital Signs and Physical Exam.	X ¹	X	X	X	X	X	X	X	X	X
Adverse Event Assessments		X ³	X	X	X	X	X	X	X	
Diary Dispensing (AE/ConMed)		X	X	X	X	X	X	X	X	X
Steroid Status		X				X	X	X	X	X
CDAI assessment	X ¹				X	X	X	X	X	X
CDAI Diary Dispensing ⁴					X	X	X	X	X	
Subject Assessments: IBDQ and SF-36	X ¹					X	X		X	
Uveitis Assessment	X ¹		X	X	X	X	X	X	X	X
ECG ¹⁰	X ¹			X		X			X	X
Hematology and Biochemistry	X ¹		X	X	X	X	X	X	X	X
Urinalysis ¹¹	X ¹		X	X	X	X	X	X	X	X
C-Reactive Protein (CRP)	X ¹					X	X	X	X	
MAP Testing Blood (PCR) with Add'l Sample for Future Use	X ¹				X	X	X	X	X	X
MAP culture from blood	X ¹					X	X		X	
Fecal calprotectin	X ¹					X	X		X	
C. difficile Testing	X ¹						X		X	
Pregnancy Test Urine	X ¹	X	X	X	X	X	X	X	X	X
Optional Colonoscopy and CDEIS/SES-CD; store images		X ⁴				X ⁵			X ⁶	
IWRS Entry		X ⁷		X ⁸			X ⁹			
Study Drug Dispensing		X	X	X	X	X	X	X		
Dispensing of Drug Administration Instructions ¹²		X	X							
Drug Return & Accountability		X ¹³	X	X	X	X	X	X	X	
Review of stool sampling technique					X	X		X		
Telephone reminder of dose escalation		Day 7	Day 21							

¹ Procedure performed as part of RHB-104-01

² Baseline visit should be scheduled once the RHB-104-01 Wk26 / RHB-104-04 Screening CDAI score has been calculated (using RHB-104-01 Wk26 hematoctrit value).

³ Ongoing AEs/ConMeds from RHB-104-01 should be captured in RHB-104-04 eCRF (AEs & ConMeds for RHB-104-01 are captured in -01 eCRF up to day prior to -04 BL)

⁴ The colonoscopy must be performed on or before the Baseline or Week 0 Visit and must not interfere with CDAI data collection. If applicable, biopsies may be collected as part of the RHB-104-01 study.

⁵ In consenting subjects, colonoscopy must be performed up to 14 days after Visit Week 16.

⁶ In consenting subjects, colonoscopy must be performed a minimum of 8 days and a maximum of 20 days prior to visit Week 52.

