6.3 Outcome Analysis

The outcome analyses will be based on all ITT subjects.

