Table 14.2.3.2	Remission at Week 16 and Week 52: Intent-to-Treat Population
Table 14.2.3.3.1	Remission at Week 52: Intent-to-Treat Population
Figure 14.2.3.3.1	Forest Plots of Week 52:Remission Odds Ratio of Parent Study Treatment RHB-104 vs Place by Selected Baseline Biomarker Categories: Intent-to-Treat Population
Table 14.2.3.3.2	Remission at Week 52 for Subjects with Baseline SES-CD ≥ 6 or Calprotectin(mcg/g) ≥ 250 or CRP (mg/dL) ≥ 2.87 Intent-to-Treat Population
Table 14.2.3.3.3	Remission at Week 52 and at least 50% Reduction in CRP or Calprotectin from Baseline: Intent-to-Treat Population: Intent-to-Treat Population
Table 14.2.3.3.4	Remission at Week 52 and at least 50% Reduction in CRP or Calprotectin from Baseline for Subjects with Baseline SES-CD ≥ 6 or Calprotectin(mcg/g) ≥ 250 or CRP(mg/dL) ≥ 2.87 : Intent-to-Treat Population
Table 14.2.3.3.5	Remission at Week 52 by Baseline MAP Buffy Coat Culture Status: Intent-to-Treat Population
Table 14.2.3.3.6	Remission at Week 52 by Week 52 MAP Buffy Coat Culture Status: Intent-to-Treat Population
Table 14.2.4.1	Time to Remission: Intent-to-Treat Population
Table 14.2.4.2	Duration of Remission: Intent-to-Treat Population
Table 14.2.4.3	Time to Response: Intent-to-Treat Population
Table 14.2.4.4	Duration of Response: Intent-to-Treat Population
Figure 14.2.4.1	Time to Remission Kaplan Meier Survival Curve: Intent-to-Treat Population
Figure 14.2.4.2	Duration of Remission Kaplan Meier Survival Curve: Intent-to-Treat Population
Figure 14.2.4.3	Time to Response Kaplan Meier Survival Curve: Intent-to-Treat Population
Figure 14.2.4.4	Duration of Response Kaplan Meier Survival Curve: Intent-to-Treat Population
Selected Other Secondary Outcome Endpoints	
Map PCR Blood Assay and MAP Blood Culture	
Table 14.2.5.1	Summary of MAP Buffy Coat Culture by Visit: Intent-to-Treat Population
Table 14.2.5.2	Shift in MAP Buffy Coat Culture from Baseline to Weeks 16, 26 and 52
Endoscopic Assessments	
Table 14.2.6.1	Baseline and Change from Baseline to Weeks 16 and 52 in SES-CD Total Scores: Intent-to-Treat Population
Table 14.2.6.2	Endoscopic Response: 25% reduction in SES-CD Total Score from baseline to

	weeks 16 and 52: Intent-to-Treat Population
Table 14.2.6.3	Endoscopic Response: 50% reduction in SES-CD Total Score from baseline to weeks 16 and 52: Intent-to-Treat Population
Quality of Life Assessment	

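### SES-CD success has no stated denominator that matches its colonoscopy-only objective, and its baseline may be a parent-study endoscopy of any age

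*SAP*

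**What the plan says.** **Who is scoped.** The visit schedule in SAP 4.1.1 lists "Optional Colonoscopy and CDEIS/SES-CD; store images" at baseline, week 16 and week 52. The protocol's study design says "Colonoscopy will be done in consenting subjects at baseline (prior to initiation of open label RHB-104" and again after 16 and 52 weeks. In both documents the heading of the endoscopic objectives restricts them to subjects who have the procedure.

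**Who is analysed.** SAP section 5 makes ITT the default for efficacy unless specified otherwise, and 6.3 states "The outcome analyses will be based on all ITT subjects". SAP 6.3.4.2 limits the SES-CD score and change summary to subjects who consent to colonoscopy. The lines that follow, on success proportions and on exact McNemar tests against CDAI remission and response, carry no such limit. Table 14.2.6.3 is titled "Endoscopic Response: 50% reduction in SES-CD Total Score from baseline to weeks 16 and 52: Intent-to-Treat Population", and the 25% table (14.2.6.2) has the same population label.

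**Missing data.** The paragraph in 6.1.3 is headed "CDAI Missing Data". It refers back to section 2.2 and then says "subjects with missing assessment will be assumed to not be in a state of remission/success for each scheduled visit (week 16, 26, or 52". The rule in 2.2.1 concerns subjects "who do not have a CDAI measurement at Week 16 will be classified as not having achieved remission at that time point". SAP 2.2.4.2, which defines SES-CD success, has no missing-data rule.

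**Baseline.** For treated subjects, 6.1.2 says "baseline is the last non-missing result prior to first dose including the data collected during the parent study for SES-CD, CDEIS, Calprotectin, CRP" and all laboratory assessments. It sets no maximum age. The schedule allows up to 21 days between screening and baseline when an initial colonoscopy is done. Its colonoscopy footnote gives a latest date (the Week 0 visit) but no earliest one.

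**The concern.** The objective asks what happened to the mucosa in people who were scoped, while the default population includes everyone who enrolled and consented. Nothing in 6.3.4.2 settles which of these is the denominator for success. The word success in the 6.1.3 rule also lets a programmer carry the missing-equals-failure rule over to endoscopy. Two programmers could follow this SAP faithfully and report very different rates.

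On the ITT reading the rate tracks consent to colonoscopy as much as healing. If unscoped subjects are also set to failure, each one in CDAI remission becomes a discordant pair (remission yes, endoscopic success no), always in the same direction. The McNemar test would then partly test who agreed to a colonoscopy.

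The baseline issue is separate. If a subject had no colonoscopy at entry to the open-label study but has one later, an older parent-study endoscopy becomes the baseline. The change then covers blinded parent treatment as well as open-label RHB-104. That earlier treatment was active in one parent group and placebo in the other, and results are summarised by parent group. The same baseline feeds the SES-CD ≥6 component of the biomarker factor in 6.3.1 and the related remission subgroup tables.

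**Working it through.** **Inputs from the documents.** N = 100; two-sided 95% exact Clopper-Pearson interval (SAP 6.1.7 and 6.3.4.2); exact McNemar (6.3.4.2); entry at parent week 26, or between weeks 26 and 52 (protocol, study population).

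**Assumed, because the documents give no figures.** Number scoped n = 20 to 80; success among scoped s = 40% (30% and 50% also shown); CDAI remission 40%, whether scoped or not; 20% of scoped pairs discordant, split evenly.

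**1. The plan's own figure.** For x successes of n, the limits are the 2.5% quantile of Beta(x, n−x+1) and the 97.5% quantile of Beta(x+1, n−x). For 50/100 they are 0.3983 and 0.6017, a width of 0.2034. This is the maximum over all x and agrees with the stated 0.203.

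**2. Success rate under the two denominators.** ITT rate = s × n / 100.

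| Scoped | Successes | Among scoped (95% CI) | Over ITT (95% CI) |
|---|---|---|---|
| 20 | 8 | 40% (19.1–63.9) | 8% (3.5–15.2) |
| 40 | 16 | 40% (24.9–56.7) | 16% (9.4–24.7) |
| 60 | 24 | 40% (27.6–53.5) | 24% (16.0–33.6) |
| 80 | 32 | 40% (29.2–51.6) | 32% (23.0–42.1) |

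With 40 scoped, s = 30% gives 12% over ITT and s = 50% gives 20%. Both columns come from the same successes, so whether their intervals overlap is not a test of anything. The point is that the second column moves with uptake while the true rate stays fixed.

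**3. McNemar if unscoped subjects are set to failure.** Let b = CDAI remission without endoscopic success, and c = the reverse. Among scoped subjects b = c = 0.10 × n, so p = 1.0. The unscoped add 0.40 × (100 − n) to b and nothing to c. The p-value is the two-sided binomial test of c out of b + c at one half.

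| Scoped | Observed b:c | Added to b | Resulting b:c | p |
|---|---|---|---|---|
| 20 | 2:2 | 32 | 34:2 | 2 × 10⁻⁸ |
| 40 | 4:4 | 24 | 28:4 | 2 × 10⁻⁵ |
| 60 | 6:6 | 16 | 22:6 | 0.004 |
| 80 | 8:8 | 8 | 16:8 | 0.15 |

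At a lower assumed remission rate of 30%, with 40 scoped, the addition is 60 × 0.30 = 18 pairs. In every row the true rates are equal, and the apparent disagreement comes only from subjects who were not scoped.

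**4. Age of the baseline.** The documents do not date the parent endoscopies. If one was done at parent entry (assumption), it is at least 26 weeks old at open-label entry. A parent week 26 endoscopy in a late entrant could be up to 52 − 26 = 26 weeks old. Either meets the rule in 6.1.2, and either can fall well outside 21 days.

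**The case against.** The case against the failure reading is strong. The 6.1.3 sentence sits under the CDAI heading and follows rules about CDAI diary days. It rests on section 2.2, where the missing-data rules cover only CDAI remission, response and maintenance. It names week 26, which has a CDAI assessment but no colonoscopy. The objectives name the scoped subset, section 5 allows exceptions to ITT, and a paired test naturally suggests that both members are observed. The ITT label is weak evidence as well: Table 14.2.6.1 carries it, although 6.3.4.2 limits that summary to consenting subjects.

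This stands to the extent that a reader should not infer that the SAP counts every unscoped subject as a failure, or that the success rates and McNemar results are therefore wrong. The text does not say so. But it does not say the opposite either. The limit to consenting subjects is attached to one summary and not to the next, and the stated default for outcomes is all ITT subjects.

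On baseline, screening is itself the parent week 26 visit, so the rule has to admit parent-study data. The protocol also anchors CDAI baseline at that visit, so a week 26 endoscopy may match it well. Only subjects without an open-label baseline colonoscopy who are scoped later are exposed, and their number is unknown. All of this is fair. It argues for a stated age limit, and against excluding parent data outright.

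A reader might also infer that success is the only mucosal result left in the tables. It is not: SES-CD score and change remain in Table 14.2.6.1, although CDEIS is listed only.

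**Conclusion.** The concern holds as a conflict between the objective and the analysis population, together with a baseline rule that has no age limit. On the stated ITT default, the SES-CD success rate is the scoped rate multiplied by uptake: an assumed 40% would be reported as anything from 8% (20 scoped) to 32% (80 scoped). If unscoped subjects were also scored as failures, McNemar p-values under equal true rates would fall from 1.0 to between 2 × 10⁻⁸ and 0.15 over that range. These figures illustrate the mechanism. They rest on assumed uptake, success, remission and discordance, and they do not predict the trial's results.

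The missing age limit is plain on the wording of 6.1.2. Its effect cannot be sized, because neither the dates of parent endoscopies nor the number of subjects affected is given.

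The reach is limited. SES-CD success belongs to the last of the SAP's four endpoint families. The primary and key secondary results do not change. The baseline rule does extend to the exploratory biomarker factor and the remission subgroups built on it.

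**What to change.** **SAP 6.3.4.2 and Tables 14.2.6.2–14.2.6.3**
- Set the success denominator at each visit to subjects with a qualifying baseline SES-CD above 0 (a percentage reduction is undefined at 0) and an SES-CD result at that visit. Show n in the title or a footnote.
- As a supportive rate, count consenting subjects who lack a follow-up result as failures.
- Limit McNemar to subjects with both SES-CD and CDAI observed at that visit.

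**SAP 6.1.3**
- State that the missing-equals-failure rule applies to CDAI outcomes only.

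**SAP 6.1.2**
- For SES-CD change and success, accept as baseline only an endoscopy within the schedule's pre-baseline window of up to 21 days, including a parent week 26 endoscopy that falls inside it.
- List older values without using them for change or success.
- Apply the same limit to the baseline SES-CD ≥6 factor, or show that factor both ways.

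**Cost.** The changes are to SAP text and table titles, with no new data. Subjects who have only an older endoscopy leave the SES-CD change and success analyses, and some may change category in the exploratory biomarker subgroup. The documents do not say how many.

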6.1.4 Conversion of time interval

In case time interval was calculated in days and need to be converted into weeks, months or years the following conversion factors need to be used:

1 week = 7 days
1 month = 30.4 days
1 year = 365.25 days

6.1.5 Pooling of Investigator Sites

All summaries and analysis will use data pooled across all investigative sites.

6.1.6 Rescue Medications Use

Subjects rescued with the following treatments or whose baseline doses/regimens are increased to treat new or unresolved CD symptoms may remain on the study drug at the discretion of the investigator and continue to be assessed at all scheduled study visits:

- Oral or rectal 5-ASA compounds
- Azathioprine or 6-mercaptopurine (6-MP) or methotrexate
- Total parenteral nutrition as treatment of CD
- Systemic or rectal corticosteroid therapy
- Anti-TNF or other biologic agent

In analyses of remission or response, subjects who initiate new treatment or increase concomitant medication to treat CD symptoms will be considered as treatment failures.

6.1.7 Determination of Sample Size

This study is anticipated to enroll 100 patients. With that number of patients, a two-sided 95% confidence interval (using the exact Clopper-Pearson method) will have a maximum width of 0.203 (i.e., +/- 10.15%) conservatively assuming the measure of interest has proportion of successes of 50%. This confidence interval will be narrower for any other possible observed proportion.

